## **6. MANAGEMENT OF ADVERSE EVENTS**

This study will collect adverse events deemed likely to have resulted from study procedures as well as serious adverse events (SAE). These will be submitted online through WebDCU™ and coded centrally using MedDRA. The severity of any study-related adverse events and any SAEs will be graded according to the Common Terminology Criteria for Adverse Events (CTCAE).

Adverse events will be reported per NIH StrokeNet Network SOP ADM12 Central Institutional Review Board (CIRB) Reporting. The Principal Investigator retains responsibility for reporting to the CIRB and the StrokeNet National Data Management Center (NDMC), which is housed in the Data Coordination Unit (DCU) in the Department of Public Health Sciences at the Medical University of South Carolina (MUSC) supports this reporting requirement. The Principal Investigator also remains responsible for all investigator duties stipulated under the NINDS Guidelines for Data and Safety Monitoring in Clinical Trials, last updated August 8, 2013. The Child Study Site Principal Investigators are responsible for reporting adverse events at their sites to the CIRB as detailed in SOP ADM12

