#### Assessments:

All subjects will undergo a brief set of assessments during the third supervised therapy session then again every 3 supervised sessions until the end of therapy. These assessments will record adverse events (which includes study-related adverse events, serious adverse events, and interval medical history), ascertain subject compliance with the unsupervised therapy sessions, document any new medications, and document the amount of any therapy (OT, PT, SLT) that the subject received outside of study procedures. At the end of supervised sessions 6 and 12, the subject will be briefly asked about any new interval medical history events. In addition, at the end of supervised session 3 and supervised session 18, the PACES, OPS scale, and Patient Satisfaction Questionnaire will each be completed. These brief assessments will be performed by the subject's Treatment Therapist.

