**5.3.3.1 Additional details for subjects randomized to in-clinic therapy:**

The 18 supervised therapy sessions will take place at the central study site. A Treatment Therapist will provide continuous supervision throughout each of these 80 minute treatment sessions. A revised treatment plan will be generated and implemented after 6 supervised sessions and again after 12 supervised sessions of therapy.

The 18 unsupervised therapy sessions will take place in the patient's home, and will be guided by an individualized booklet generated and printed by the Treatment Therapist and distributed to the subject during the first in-clinic therapy visit. The content of the unsupervised therapy sessions will be matched to the same exercise and training components provided during the subject's in-clinic supervised therapy sessions. After 6 supervised sessions and again after 12 supervised sessions of therapy, the booklet guiding the unsupervised therapy session will be returned to the therapist, at which time a new booklet will be provided to the subject, containing a revised therapy plan. At the start of each of the 18 unsupervised sessions, all subjects will receive 5 minutes of stroke education. As with the other content of the unsupervised sessions, stroke education will be delivered by booklets provided by the Treatment Therapist during a supervised therapy session. Using a large Helvetica font, a multiple-choice question is presented, the patient marks his/her answer, then the patient is provided with the correct answer along with a brief explanation. This is repeated four times, for a total of five questions at each unsupervised session.

If there are any unsupervised therapy sessions completed after a subject's final supervised therapy session, the Treatment Therapist will call the patient at home and collect data on compliance for any such sessions.

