**5.3.3.2 Additional details for subjects randomized to telerehabilitation therapy:**

A member of the study team will deliver the telerehabilitation system to the subject's home, set it up, confirm functionality, and review use of the system with the subject. Note that the telerehabilitation system will not operate for any process apart from telerehabilitation at any time, and will only provide telerehabilitation for the number of assigned minutes.

The 18 supervised therapy sessions will be performed by the subject, at home, using the telerehabilitation system. At the beginning of each supervised session, a Treatment Therapist at the central study site will initiate a videoconference with the subject's telerehabilitation system.

The Treatment Therapist will then supervise the subject, using a structured approach, for a 30 minute period during which the therapist will observe the patient performing assigned home-based telerehabilitation exercises and tasks, answer questions, review the treatment plan, and perform the brief study assessments during selected days. After 30 minutes, the therapist will disconnect from the videoconference, then the subject will complete the remaining 50 minutes of therapy, including a brief break, guided by the telerehabilitation system.

The 18 unsupervised therapy sessions will also be performed by the subject at home using the telerehabilitation system. There will be no contact with a study therapist during these sessions. Instead, all 80 minutes of therapy will be guided only by the telerehabilitation system. At the start of each of the 18 unsupervised sessions, subjects in the telerehabilitation group will receive 5 minutes of stroke education. As with the other content of the unsupervised sessions, stroke education will be delivered by the telerehabilitation system. A 5-level multiple-choice question is presented on the computer screen, the patient enters his/her answer, and then the patient is provided with the correct answer along with a brief explanation. This is repeated four times, for a total of five questions at each unsupervised session. All steps (read, answer, move forward, etc.) are timed, recapitulating the approach used successfully in our pilot study.

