### 8.2 Summarization of safety data:

This is a low-risk interventional study, and the FDA has determined it to be a non-significant risk device study. As a result, no data and safety monitoring board is planned. Adverse events will be regularly assessed, and those considered likely attributable to study procedures will be documented, as will all SAEs. Within each treatment arm, the frequency and percentage of study-related adverse events and SAEs will be tabulated and reported by grade, system organ-class, and preferred term. Any study-related adverse events will be summarized as those leading to a specific intervention, those leading to study discontinuation, and by severity. Any SAEs will be reported similarly.

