**14.6. Describe any potential RISKS OR DISCOMFORTS in detail.**

Overall the risks related to this study are small. One potential risk related to study participation is breach of security for data handling, which could potentially result in a loss of privacy of sensitive medical/neurological information. A number of steps to safe guard Information will be taken including the use of locks for files and use of passwords for computer files to maintain this risk as extremely small. All computer signals from the subject's home to the lab will use methods that maximize security. The computer provided for home use will contain no personal information. Any data related to a subject's arm motor function is labeled with the subject ID number and has no identifying information.

A second potential source of potential risk is the telerehabilitation system. The risk of hardware is expected to be extremely small. The risk of daily participation for 6 weeks is also expected to be extremely small. Nonetheless, some of the methods to be pursued in the proposed study are untested and so could expose the patient to unexpected risks. We will remain sentinel for these by using close-ended and open-ended questions during live and during telecommunication call interviews with patients.

A third potential source of potential risk is the behavioral testing. This can produce fatigue, a possibility for which trial investigators and staffs will be trained to remain sentinel. Procedure training will reinforce the use of offering subjects breaks for rest, snacks and bathroom use routinely.

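### The non-serious rows of the by-arm safety table count only events judged likely due to study procedures, so they cannot be read as incidence, although unfiltered interval history is already recorded

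*Combined protocol and SAP*

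**What the plan says.** **The filter.** Section 6 (Management of Adverse Events) states: "This study will collect adverse events deemed likely to have resulted from study procedures as well as serious adverse events (SAE". Section 8.2 (Summarization of safety data) says events will be assessed regularly, but that "those considered likely attributable to study procedures will be documented, as will all SAEs". For the table, within each arm, "the frequency and percentage of study-related adverse events and SAEs will be tabulated and reported by grade, system organ-class, and preferred term". No table of non-serious events regardless of cause is planned.

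**What is recorded at the checks.** Section 5.3.3, under Assessments, says of the checks made every three supervised sessions: "These assessments will record adverse events (which includes study-related adverse events, serious adverse events, and interval medical history". The subject's Treatment Therapist, who knows the assigned arm, carries them out. Sections 5.3.4 (Post-Therapy Visit) and 5.3.5 (Day 30 Follow Up) define adverse event recording in the same way; there the recorder is the blinded Assessment Therapist. The data collection schedule in Section 5.3 marks adverse events at all eight of these points, in both arms.

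**What the study says it is looking for.** Section 14.6 concedes that "some of the methods to be pursued in the proposed study are untested and so could expose the patient to unexpected risks" and undertakes to look for such risks by questioning subjects with both closed and open questions.

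**The concern.** The plan asks subjects about new events on a fixed schedule, then keeps a non-serious event for coding, grading and tabulation only if it has passed a causality judgement. No section says who decides that an event is likely due to study procedures, or by what criteria. During the therapy weeks the person recording the event is unblinded.

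A non-inferiority result for home therapy will be read beside its safety table, and a reader will naturally take the non-serious rows as event rates by arm. They are not. If unattributed events are never coded, incidence and attribution cannot be separated afterwards. An effect that nobody expected, which Section 14.6 says the study will watch for, reaches the table only if it is linked to study procedures when reported. Section 8.2 also plans no data and safety monitoring board, so no such board would look behind the table.

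**Working it through.** The plan states no adverse event rate, attribution rate or safety precision, so there is no figure to reproduce. The check compares the sections and then shows what follows from the filter.

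**1. Sections side by side**

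- *Collected:* Section 6 has likely-related non-serious events plus all SAEs. Section 5.3.3 (Assessments), 5.3.4 and 5.3.5 have study-related events, SAEs and interval medical history.
- *Tabulated:* Section 8.2 has study-related events and SAEs only. Neither Section 6 nor 8.2 provides coding, grading or a by-arm summary for interval medical history.
- *Sought:* Section 14.6 includes unexpected risks.

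The second set of sections elicits more than the first keeps.

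**2. What the non-serious rows estimate**

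Let p be the true proportion of an arm with a given non-serious event, and a the probability that the event is judged likely due to study procedures. Allowing one event per subject for simplicity:

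- tabulated proportion = p × a
- tabulated ratio, telerehabilitation to in-clinic = (p_T / p_C) × (a_T / a_C)

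The rows equal incidence only if a = 1. The ratio is right only if a is the same in both arms. For SAEs no attribution is required, so the filter does not affect them.

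**3. Illustration**

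All values of p and a below are assumptions. The 62 per arm is the target in Section 8, Determination of sample size.

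| Assumed p (T, C) | Assumed a (T, C) | Tabulated (T, C) | Expected subjects of 62 (T, C) | Tabulated ratio | True ratio |
|---|---|---|---|---|---|
| 0.20, 0.20 | 0.50, 0.50 | 0.10, 0.10 | 6.2, 6.2 | 1.0 | 1.0 |
| 0.20, 0.20 | 0.50, 0.25 | 0.10, 0.05 | 6.2, 3.1 | 2.0 | 1.0 |
| 0.20, 0.20 | 0.25, 0.50 | 0.05, 0.10 | 3.1, 6.2 | 0.5 | 1.0 |
| 0.30, 0.15 | 0.50, 0.50 | 0.15, 0.075 | 9.3, 4.65 | 2.0 | 2.0 |
| 0.30, 0.15 | 0.25, 0.50 | 0.075, 0.075 | 4.65, 4.65 | 1.0 | 2.0 |

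In rows 2 and 3, p cancels from the ratio, so the false twofold difference is the same for any common p; with p from 0.10 to 0.40, row 2 runs from 3.1 against 1.55 subjects to 12.4 against 6.2. Row 4 shows that equal attribution keeps the ratio but halves the absolute difference, from 15 to 7.5 percentage points. Row 5 shows a true excess disappearing. Unequal attribution is shown in both directions because the documents support neither over the other.

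**The case against.** The strongest reply is that this is a deliberate and proportionate choice. Section 8.2 opens by calling the study low-risk and citing the FDA's non-significant-risk determination, and Sections 14.1 and 14.3 say the same. Serious events, which matter most, are captured whatever their cause. No aim contains a safety hypothesis, and Section 8.2 plans description within each arm, not a test between arms. All of that stands. It confines the point to the non-serious rows and makes it a matter of reporting. It does not turn those rows into incidence.

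A reader might infer that the filter makes telerehabilitation look safer. In-clinic, "A Treatment Therapist will provide continuous supervision throughout each of these 80 minute treatment sessions"; in telerehabilitation, "After 30 minutes, the therapist will disconnect from the videoconference". The documents do not support that inference:

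- Events are asked about on the same schedule in both arms, and symptoms such as pain are reported when asked, so observed minutes are not the route of detection. Those minutes also include breaks.
- Section 11.1 intends one Treatment Therapist per site to treat both arms, and makes the site lead investigator responsible for reporting. Nothing says the therapist makes the causality judgement.
- Recording at the last two visits is blinded.
- An unfamiliar home device could equally attract more attribution.

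A reader might also see a contradiction in Section 5.3.3, which adds: "At the end of supervised sessions 6 and 12, the subject will be briefly asked about any new interval medical history events". It does not say that history is asked only then, and the schedule marks adverse events at all six therapy-period checks. This is redundant wording, at most an editorial query.

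**Conclusion.** The point holds for the non-serious rows of the by-arm table and for nothing wider. As written, those rows are incidence multiplied by an attribution probability that has no stated criteria and, during therapy, applies to events recorded by someone who knows the arm. Sections 6 and 8.2 do not match the broader definition of recorded adverse events in Sections 5.3.3 to 5.3.5, and the sections must be reconciled.

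The documents give no basis for the size or direction of any between-arm distortion. The table of assumed values shows the mechanism only, and it would be wrong to say that the comparison favours either arm. The SAE rows and the primary efficacy analysis are unaffected. The change is worth making because events left uncoded cannot easily be recovered later and the remedy fits the existing visit schedule.

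**What to change.** - **Section 8.2:** add a descriptive by-arm table of all new or worsened events captured as adverse events or interval medical history, regardless of attribution. Code them in MedDRA, grade them by CTCAE where the recorded detail allows, and show likely-related events as a labelled subset. No between-arm test is needed.
- **Section 6:** make relatedness a recorded field, not a condition for collection, and state who assigns it and by what criteria. Bring the wording into line with Sections 5.3.3 (Assessments), 5.3.4 and 5.3.5.
- **Section 5.3.3, editorial:** say whether the question at supervised sessions 6 and 12 is additional to the regular checks.

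**Cost:** modest coding work and one more table, with no new visits. More background events will be listed in both arms. The documents do not say how much detail interval-history entries carry, so some may be codable but not gradable.

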## **7. CRITERIA FOR PREMATURE STUDY TERMINATION**

### **Subject Removal from Therapy:**

As participation in the "Telerehabilitation in the Home versus Therapy In-Clinic for Patients with Stroke" trial is voluntary, the subject may decline study therapy at any time. In addition, the treating investigator may stop study therapy if there is a safety concern. In either case, the subject will continue to be followed through the 30 Day Follow Up visit, unless informed consent is withdrawn.

### **Subject Withdrawal:**

The subject has the right to voluntarily withdraw from the study at any time for any reason without prejudice to his/her future medical care by the physician or at the institution. For the occasional subject who withdraws consent, the date and reason for consent withdrawal should be documented. Subject data will be included in the analysis up to the date of the consent withdrawal. The distinction must be made between subjects who withdraw consent versus those who decline study therapy.

### **Procedure for Discontinuation:**

The procedure to be followed at the time a subject withdraws consent from the trial:

- Check for the development of SAEs or study-related adverse events.
- Complete the End-of-Study form; include an explanation of why the subject is withdrawing consent.

### **Subject Lost to Follow-Up:**

In the event that all possible attempts to locate the subject have failed, all efforts made by the investigator to contact the subject should be documented and the subject will be coded as lost to follow-up.

## 8. STATISTICAL CONSIDERATIONS, DATA ANALYSIS AND DATA MONITORING

In the study, populations used for testing comparable efficacy, the non-inferiority margin proposed for determining comparable efficacy, the statistical procedures used for summarizing and testing the primary and secondary comparable efficacy endpoints, and sample size justification for the proposed study. All analyses are two-tailed and use  $\alpha=0.05$ .

### 8.1 Analysis of populations:

Primary efficacy analyses will be conducted on the Intent-To-Treat (ITT) Population, defined as all subjects who are randomized. Sensitivity analyses for efficacy will also be conducted on the Per-Protocol Population, defined as all subjects who complete assigned activities for at least 40 minutes at 15 or more of the 18 supervised therapy sessions over a period of time extending no more than 8 weeks. In ITT analysis, for missing data such as due to subject lost to follow-up, multiple imputation using all available evaluation data will be utilized. No interim analysis is planned.

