### **5. 4. Prohibited Therapy/Medication**

Subjects may continue all therapy outside of study procedures as long as this non-study therapy does not interfere with the subject's fulfillment of study therapy and testing. The amount of any such outside therapy will be recorded at regular intervals.

The study protocol does not permit application of Botox to arm, leg, or trunk until after the 30 Day Follow Up visit is completed.

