### 13.2. Inclusion/Exclusion Criteria:

#### Inclusion criteria

1. Age  $\geq 18$  years at the time of randomization
2. Stroke that is radiologically verified, due to ischemia or to intracerebral hemorrhage, and with time of stroke onset 4-36 weeks prior to randomization
3. Arm motor FM score of 22-56 (out of 66) at both the Screening Visit and Baseline Visit
4. Box & Block Test score with affected arm is at least 3 blocks in 60 seconds at the Screening Visit
5. Informed consent signed by the subject
6. Behavioral contract signed by the subject

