#### Exclusion criteria

1. A major, active, coexistent neurological or psychiatric disease, including alcoholism or dementia
2. A diagnosis (apart from the index stroke) that substantially affects paretic arm function
3. A major medical disorder that substantially reduces the likelihood that a

- subject will be able to comply with all study procedures
4. Severe depression, defined as GDS Score >10
  5. Significant cognitive impairment, defined as Montreal Cognitive Assessment score < 22
  6. Deficits in communication that interfere with reasonable study participation
  7. A new symptomatic stroke has occurred since the index stroke that occurred 4-36 weeks prior to randomization
  8. Lacking visual acuity, with or without corrective lens, of 20/40 or better in at least one eye
  9. Life expectancy < 6 months
  10. Pregnant
  11. Receipt of Botox to arms, legs, or trunk in the preceding 6 months, or expectation that Botox will be administered to the arm, leg, or trunk prior to completion of the 30 Day Follow Up Visit
  12. Unable to successfully perform all 3 of the rehabilitation exercise test examples
  13. Unable or unwilling to perform study procedures/therapy, or expectation of non-compliance with study procedures/therapy
  14. Concurrent enrollment in another investigational study
  15. Non-English speaking, such that subject does not speak sufficient English to comply with study procedures
  16. Expectation that subject cannot participate in study visits
  17. Expectation that subject will not have a single domicile address during the 6 weeks of therapy, within 25 miles of the central study site and with Verizon wireless reception.\*\*

\*\*A site may enroll a person who does not meet exclusion criterion # 17 if this is specifically approved by the site's study PI.

\*\*Because Montreal Cognitive Assessment scores may be difficult to interpret for patients with aphasia, at the discretion of the site's study PI, exclusion criterion #5 ("MoCA score cannot be <22") can be waived.

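### The Per-Protocol set, the only sensitivity population for the non-inferiority claim, has no criterion for breaches of entry criteria or for prohibited Botox

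*Combined protocol and SAP*

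**What the plan says.** Section 8.1 sets two analysis populations. For the first: "Primary efficacy analyses will be conducted on the Intent-To-Treat (ITT) Population, defined as all subjects who are randomized". For the second: "Sensitivity analyses for efficacy will also be conducted on the Per-Protocol Population". Its definition reads: "Per-Protocol Population, defined as all subjects who complete assigned activities for at least 40 minutes at 15 or more of the 18 supervised therapy sessions". An 8-week limit on those sessions also applies. No other analysis population is named. We found no list of major protocol deviations, and no rule for reviewing deviations before analysis.

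Elsewhere the protocol sets conditions that the Per-Protocol definition does not mention:

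- Section 13.2, inclusion criterion 3, requires "Arm motor FM score of 22-56 (out of 66) at both the Screening Visit and Baseline Visit". Criterion 2 requires a radiologically verified stroke with onset 4-36 weeks before randomisation, and criterion 4 a Box & Block score of at least 3.
- Section 13.2 excludes another diagnosis that substantially affects the paretic arm (criterion 2), cases where "A new symptomatic stroke has occurred since the index stroke" (criterion 7), and Botox in the previous 6 months or expected before the 30 Day Follow Up Visit (criterion 11).
- Section 5.4 states that the protocol "does not permit application of Botox to arm, leg, or trunk until after the 30 Day Follow Up visit is completed".

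The footnotes to section 13.2 let the site's PI approve exceptions to exclusion criterion 17 and waive criterion 5. No footnote allows a waiver of the criteria listed above.

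**The concern.** The trial succeeds if telerehabilitation is shown not to be worse than in-clinic therapy by 2.05 points or more. In that setting, deviations that make the arms look alike favour the conclusion sought. A Per-Protocol analysis is the usual check that an ITT finding of non-inferiority was not produced that way.

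Here that check covers one kind of deviation: not completing the supervised sessions in time. Subjects who should not have been randomised, or who received a treatment that the protocol bars, are treated in the Per-Protocol set exactly as in ITT. If the two analyses agree, a reader may take the result as robust to protocol deviations in general. The definition supports only the narrower statement that it is robust to non-completion of supervised therapy.

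**Working it through.** **Step 1. Trace subjects through the definition.** The rule has three parts: at least 40 minutes of assigned activities, at 15 or more of 18 supervised sessions, within 8 weeks. Applied to hypothetical subjects:

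- Randomised in error with baseline Fugl-Meyer outside 22-56, 16 sessions in 7 weeks: included.
- Eligible, given Botox before the 30 Day visit, 15 sessions in 8 weeks: included.
- Enrolled under an approved exception to criterion 17, 18 sessions in 6 weeks: included, and rightly so.
- Eligible with no deviation, 14 sessions: excluded. Any threshold does this, and it is not the defect.

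**Step 2. What separates the two sets.** ITT is everyone randomised. Per-Protocol is ITT minus those who fail the session rule. The first two subjects above are therefore in both sets, and comparing the two results carries no information about them.

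**Step 3. Are the data there to do better?** The section 5.3 schedule records eligibility criteria at Screening, Fugl-Meyer at Screening and Baseline, and medications at every assessment from Screening to the 30 Day visit. If Botox is recorded among the medications (an assumption about how the form is filled in), nothing new has to be collected.

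**Step 4. The plan's own figures.** Section 8 gives a margin of 2.05, SD 4.0, a 95% interval (one-sided 0.025), 80% power and 62 per arm. With no true difference,

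n per arm = 2 × 4.0² × (1.960 + 0.842)² / 2.05² = 251.2 / 4.2025 = 59.8, so 60.

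The t-based calculation gives 61. Power at 62 per arm is 0.81 by either method. Also 124 / 0.80 = 155. The sample size reproduces and is not in dispute.

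**Step 5. Illustration of dilution.** Assume that the true difference is −2.05 but a fraction f of the Per-Protocol set shows no arm difference. The documents give no f. With 62 per arm (the planned number with 30 Day data, used as an assumed Per-Protocol size), SE = 4.0 × √(2/62) = 0.718, and

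false non-inferiority rate = Φ(2.05 × f / 0.718 − 1.960).

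- f = 0: 2.5%
- f = 5%: 3.5%
- f = 10%: 4.7%
- f = 20%: 8.2%
- f = 30%: 13.5%

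Nothing in the documents points to the upper values. In points, 3 such subjects out of 62 in each arm shrink the difference by 3 × 2.05 / 62 = 0.10, about 5% of the margin.

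**Step 6. What a smaller set costs.** At a true difference of 0, normal-approximation power is 81% with 62 per arm, 77% with 56, 73% with 50 and 63% with 40. These Per-Protocol sizes are also assumed.

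**The case against.** The strongest defence is that in a therapy trial, not receiving the therapy is the obvious source of dilution, and the definition targets exactly that. ITT is primary, so nothing here changes the main result. Eligibility breaches should also be rare: section 5.3.2 puts randomisation after final eligibility is determined, and baseline Fugl-Meyer and time since stroke feed both the covariate-adaptive randomisation (section 5.2) and the ANCOVA. This stands as a reason to keep the point modest. It does not fill the gap. Rarity is not documented, and covariate adjustment does nothing for Botox.

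A reader might infer several stronger things that the documents do not support:

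- **That the set is defined by attendance alone.** It also requires 40 minutes of completed activity per counted session and sets an 8-week limit.
- **That waived subjects are wrongly retained.** Section 13.2 itself permits the exceptions to criteria 5 and 17, so these subjects were enrolled according to protocol.
- **That a stroke after randomisation is a retained violation.** Exclusion criterion 7 governs eligibility. A later stroke is an intercurrent event with no stated rule. Removing subjects for it is a debatable choice of estimand that brings its own selection bias.
- **That the effect is a sizeable share of the margin.** Three subjects in one arm, each 5-10 points off course, would move that arm's mean by 3 × 5/62 = 0.24 to 3 × 10/62 = 0.48, or 12-24% of 2.05. The 5-10 points, the count and the one-sided placement are all invented. The shift could go either way, and it is not the dilution mechanism that gives the concern its force.
- **That a subject randomised at a score of 60 proves a ceiling problem because 66 − 60 = 6 is below 6.85.** The 6.85 is an assumed group mean, not a target for an individual, and nothing suggests that such a subject is likely.

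**Conclusion.** The point holds in a limited form. Followed exactly, section 8.1 counts as per protocol any subject who meets the session rule, including one who breached an entry criterion with no waiver or who received Botox before the 30 Day visit. Because this is the only sensitivity population, agreement with ITT would not address those deviations.

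The conclusion rests on reading the definition as complete, and on our finding no other section that adds to it. The number of affected subjects cannot be derived from the documents, and so neither can the size or direction of any effect. The rates in step 5 show how dilution would act under assumed fractions and do not estimate what will happen here. The point does not show that the primary analysis is biased or that the sample size is wrong. It is a conventional and inexpensive improvement to a stated rule.

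**What to change.** Extend the Per-Protocol definition in section 8.1 with a clause to this effect: *and who met inclusion criteria 2-4 and none of exclusion criteria 2, 7 and 11 at randomisation, and received no Botox (section 5.4) before the 30 Day Follow Up Visit.* State that membership is fixed before database lock, without reference to treatment arm or outcome.

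Subjects enrolled under the permitted waivers of criteria 5 and 17 stay in. A stroke after randomisation should not be made a Per-Protocol exclusion through this change.

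The cost is a wording change and a slightly smaller Per-Protocol set, with the modest loss of precision shown in step 6. The primary ITT analysis, sample size, data collection and patient care are unchanged.
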